#### **Hypothesis: Acute Effect**

##### **Hypothesis 1.1**

Distress associated with pain as measured by the West Haven-Yale Multidimensional Pain Inventory (WHYMPI) (affective subscale) and pain anxiety symptom scale (PASS-20) will decrease after ten (10) days of active but not sham stimulation.

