### **C2. Study Design**

The study includes a screening visit, ten (10) study treatment session visits on consecutive weekdays and a follow-up phone call, approximately six (6) weeks after the last study visit. The ten study visits will occur at Butler Hospital and will take between two (2) to two and half hours (2 ½) hours. The total duration of this study for the participant is expected to be up to approximately twenty- four (24) hours; this includes the consent process, screening and eligibility assessments and ten research visits which will include the study treatment, tDCS, completion of study related questionnaires, and the follow-up phone call.

Half of the participants will receive only sham stimulation for all treatment days (days where tDCS is applied) and half will receive only active stimulation; this will be randomly assigned. Comprehensive measures of distress resulting from CLBP will be administered to assess both the short and longer term effects of tDCS treatment. Participants and research staff administering outcome scales will be blinded to active vs. sham tDCS.

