**Emotional Distress:** Investigators will employ a battery of measures to determine the degree to which participants experience emotional distress resulting from pain. First, the affective sub-scale of the WHYMPI will be used to measure negative emotion related to pain. Second, the General Anxiety Disorder 7-item scale (GAD-7) will be used to assess general anxiety symptoms. Third, the Patient Health Questionnaire (PHQ-9) will be used to assess depressive symptoms (Kroenke 2001). The PHQ-9 is a quick self-report measure demonstrating reliability and validity in primary care settings (Spitzer 1999). Lastly, we will include the short form of the pain anxiety symptom scale (PASS-20) to measure fear and avoidance behavior related to pain (McCracken & Dhingra 2002).

**Patient Expectation and Satisfaction:** We will assess treatment credibility and patient expectations for treatment success using the Credibility Expectancy Questionnaire (CEQ; Devilly & Borkovec 2000). The Client Satisfaction Questionnaire-8 (CSQ-8; Larsen, Attkisson, Hargreaves, & al., 1979), an 8-item scale, will be used at post-treatment to assess patient satisfaction with the treatment. This scale has acceptable psychometric properties (Nguyen, Attkisson, & Stegner, 1983).

**Psychiatric History:** Drug related problems, exclusionary disorders, and other non-exclusionary psychiatric disorders will be assessed with a structured psychiatric interview, the Mini International Neuropsychiatric Interview (MINI). This is a validated interview designed to screen for Axis I disorders. Potential participants that are determined by the MINI to have lifetime diagnoses of bipolar disorder, schizophrenia, other chronic psychotic condition(s), and/or drug or alcohol dependence will be considered screen failures.

Date most recently revised (m/d/y): 03/03/2015

Protocol Version (if applicable): 5.0

**Sleep Measure:** An in-office assisted report of sleep will be used to assess quantity and quality of sleep throughout the ten testing days of the study. The questions used to assess sleep have been based on those used in the 1992 Carskadon Sleep-Wake Diary.

*Table 1. Schedule of Assessments*

	Purpose	Consent and Screen	First Day of Week One Session 1	Pre/Post Treatment Session 1-10	End of Week One and Two Session 5 & 10	Six Week Follow-up
Pain Severity Defense & Veterans Pain Rating Scale (DVPRS)	I, O	X	X	X	X	X
Pain Interference WHY-MPI RMDQ	O O		X X		X X	X X

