The participant will then receive either the sham or active tDCS stimulation based on their random group assignment for twenty minutes (tDCS details are below). Following tDCS stimulation, only the DVPRS will be repeated. This measure will be used to determine whether immediate pain relief following stimulation occurs. Lastly, in order to monitor the effectiveness of the blind, participants will be asked to guess which treatment, active or sham, they received.

On subsequent treatment days, the DVPRS will be repeated before and after stimulation and the Sleep Measure will be repeated before stimulation. At the end of the first week of treatment, session five, in addition to the DVPRS and the Sleep Measure, the WHY-MPI, RMDQ, CPAQ-8, PHQ-9, GAD-7, and the PASS, will be repeated. During the second week, the DVPRS will again be administered before and after each treatment, and the Sleep measure will be repeated before stimulation.

On the final day of treatment, in addition to the DVPRS and the Sleep Measure, the WHY-MPI, RMDQ, CPAQ-8, PHQ-9, GAD-7, CEQ, CSQ-8, and the PASS, will be repeated.

Date most recently revised (m/d/y): 03/03/2015

Protocol Version (if applicable): 5.0

Follow-up assessments will occur by phone approximately six (6) weeks after the last tDCS treatment session and will consist of these same measures as session ten.

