#### D. Material Inducements

Date most recently revised (m/d/y): 03/03/2015

Protocol Version (if applicable): 5.0

Compensation for time and effort will be offered for the measures administered in this study. Participants will receive \$60 as compensation for participation if they complete all 10 sessions of tDCS treatment. If the participants withdraw from the study before finishing, they will receive \$6 per session for each session in which they participated regardless if they were able to complete the full session.

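### Outcome timing follows the sessions received: a participant who stops early has no session-10 score, and the session-10 scales are not placed after the tenth stimulation

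*Combined protocol and SAP*

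**What the plan says.** Hypotheses 1.1 and 1.2 state the acute effect in terms of stimulation received: the scores "will decrease after ten (10) days of active but not sham stimulation". C2 plans "ten (10) study treatment session visits on consecutive weekdays and a follow-up phone call, approximately six (6) weeks after the last study visit".

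Table 1 schedules the full battery at session 1, in a column headed "End of Week One and Two Session 5 & 10", and at the six-week follow-up. The visit text in C3 describes the last of the on-site batteries this way: "On the final day of treatment, in addition to the DVPRS and the Sleep Measure, the WHY-MPI, RMDQ, CPAQ-8, PHQ-9, GAD-7, CEQ, CSQ-8, and the" (the pain anxiety scale ends the list). It then sets the phone follow-up "approximately six (6) weeks after the last tDCS treatment session and will consist of these same measures as session ten".

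The protocol expects that some participants will not finish. Section D of Human Subjects lets participants stop at any time. Material Inducements pays those who withdraw $6 "for each session in which they participated regardless if they were able to complete the full session". Section D.1B says in two places that a participant judged on clinical grounds to have been harmed is withdrawn from the study. C4 names (M)ANOVA, repeated-measures and mixed linear models. It has no rule for missed or off-schedule assessments and does not say which participants are analysed.

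**The concern.** The battery carries the outcomes of Hypotheses 1.1 and 1.2, and it has a defined time only for someone who reaches session 10. If stopping is related to arm, the end-of-treatment comparison is between those who stayed, and randomisation no longer protects it.

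The arms plausibly differ in what they feel. Active stimulation runs for 20 minutes at up to 2 mA, whereas sham is 40 seconds at 1 mA followed by almost no current. D.1B also reports that cathodal current irritated the skin most.

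The second gap affects completers as well. If the scales are filled in before the tenth stimulation, the endpoint measures the effect of nine. If the order varies between participants, it is a mixture of the two.

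**Working it through.** The plan states no rate, power or error figure on this point. The check is therefore a reading of the schedule, a calendar count and one line of arithmetic.

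**1. Participants who complete as scheduled.** With ten consecutive weekdays from a Monday, session k falls on calendar day k for k = 1 to 5 and on day k + 2 for k = 6 to 10. Session 10 is day 12. Six weeks later is 12 + 42 = day 54. For a start on any other weekday the figures are day 14 and day 56. Every on-site visit after screening is a treatment visit, so the last visit and the last stimulation share a date. The labels do not conflict here.

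**2. Participants who stop after session k (Monday start).**

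| Last session k | Calendar day | Days before scheduled session 10 | Six weeks after last session |
|---|---|---|---|
| 1 | 1 | 11 | day 43 |
| 3 | 3 | 9 | day 45 |
| 5 | 5 | 7 | day 47 |
| 6 | 8 | 4 | day 50 |
| 9 | 11 | 1 | day 53 |
| 10 | 12 | 0 | day 54 |

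Session 10 never occurs for k = 1 to 9. The battery is planned only at sessions 1, 5 and 10 and at follow-up. Someone who stops after sessions 1 to 4 has no on-treatment score beyond baseline, and someone who stops after sessions 5 to 9 has session 5 at most. If the call is made at all, counting from the last session puts it 1 to 11 days earlier after baseline than for a completer. The plan does not say whether a withdrawn participant is called.

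**3. Size of the loss.** C1 plans 10 per arm. One loss is 1/10 = 10% of an arm and two are 2/10 = 20%. Let C be the mean of those observed at session 10, and S the mean that the m participants who stopped would have had on the same date. The mean of all n in the arm is [(n − m)C + mS]/n, so the observed mean is off by (m/n)(C − S). With n = 10 this is 0.1(C − S) for m = 1 and 0.2(C − S) for m = 2. It cancels between arms only if both arms lose the same share with the same gap.

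**4. Order at session 10.** At session 1 the battery comes before stimulation, and only the DVPRS is repeated afterwards. On later days the DVPRS is placed before and after stimulation and the Sleep Measure before it. For sessions 5 and 10 the other scales are said only to be repeated that day. Given before stimulation at session 10, they follow 10 − 1 = 9 stimulations; given after, they follow 10.

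**The case against.** A reader might infer that the plan gives conflicting definitions of the acute endpoint. The documents do not support that. The hypotheses count days of stimulation, not calendar days. Table 1 restricts the CEQ and CSQ-8 repeat to session 10, the visit text puts it on the final day, and the next sentence refers back to session ten. They are one visit.

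A reader might also infer that someone who stops at session 3 gets a day-3 endpoint under one passage and a day-10 endpoint under another. Neither exists: ordinary treatment days carry only the DVPRS and Sleep Measure, and that person never has ten days of stimulation.

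The two follow-up anchors, last visit and last stimulation, separate only if the last attended visit has no stimulation, for example because the scalp check prevents it. A missed session that is made up at the end moves the tenth stimulation to day 15 but leaves session 10, final day and both anchors in agreement. Device termination or an incomplete session does not change the session number.

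The evidence that stopping would differ by arm is also thin. The irritation remark comes from tests on the skin of the arm, reports nothing worse than tingling and transient redness, and does not compare active with sham. Estimates of how many participants would miss a session need a per-session rate that the documents do not supply, so none is used here. The study also calls itself exploratory.

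These arguments remove the charge of contradiction. They do not supply an assessment for people who stop, or an order for the session-10 scales. Exploratory status explains the absence of a power analysis but does not make an endpoint time unnecessary. The statement that CSQ-8 is used at post-treatment does not settle the order of the WHYMPI, PASS-20 and RMDQ.

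**Conclusion.** The point holds as two gaps in the rules, not as inconsistent definitions.

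- **Early stopping.** Outcome collection depends on sessions received. Each participant lost is 10% of an arm, and the observed arm mean moves by a tenth of the gap between those who stay and those who stop. Whether this happens, and whether it differs by arm, is unknown because the plan gives no stopping rate. A difference by arm is plausible but not shown.
- **Order at session 10.** The acute endpoint may follow nine stimulations or ten. This can affect all 20 participants and needs no assumption about dropout. The size of the resulting difference in scores cannot be derived from the documents.

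Both are worth correcting because the correction is cheap and the arms are small.

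**What to change.** - **C3, visit text.** State that the session-10 WHYMPI, PASS-20, RMDQ and the rest of the battery are given after the tenth stimulation.
- **Participants who stop stimulation.** Separate stopping stimulation from withdrawing consent to be assessed. For those who stop but still consent, collect the same battery on the originally scheduled session-10 date, by phone if they do not attend, and make the follow-up call on its originally scheduled date. Reconcile the withdrawal wording in D.1B with this. The clinical decision to stop is not affected.
- **C2 and C3, follow-up.** Use one wording for the six-week anchor, with a visit window wide enough to cover made-up sessions.
- **C4.** Analyse all participants in their assigned arm, using the scores collected at these times.

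The cost is protocol wording and a few phone assessments, a mode already used for the follow-up battery. There are three drawbacks. Phone and in-person scores will be mixed for some participants. A battery given straight after stimulation also picks up any immediate effect of that session. The estimate becomes the effect of assignment to active or sham, not of ten completed sessions.

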### **tDCS Details**

Equipment used for tDCS Intervention, the Neuroconn DC-STIMULATOR PLUS, is a micro-processor-controlled constant current source. tDCS is a non-invasive procedure in which a device sends a small Direct Current (DC) across the scalp to modulate brain function. A low-level current from the positive electrode, anode, is sent to the negative electrode, cathode. When the extremely low level current passes from the anode to the cathode, it may simultaneously increase the activity of the brain by the anode and decrease the activity of the brain near the cathode. The DC-stimulator meets the highest safety standards thanks to (hardware- and software-based) multistage monitoring of the current path. It continuously monitors electrode impedance and it can detect insufficient contact with the skin and automatically terminate stimulation to reliably prevent participant injury.

The FDA recognizes the tDCS device as a non-significant risk device. During each treatment session, tDCS will be applied to the scalp using a Neuroconn DC- Stimulator.

*Figure 1. tDCS device*

Stimulation will be applied to the participant's skull using metal electrodes seated in a flat, slightly perforated rectangular sponge pocket. The sponges will be soaked in normal saline (0.9% NaCl) and affixed to the head on intact skin (after the scalp skin is cleaned with an alcohol prep pad) and held in place with a custom tDCS specific rubber headband. One set of sponges will be used for each participant. Standard conductive water based gel (Spectra 360 electrode gel) will be applied to the sponge (between the scalp and the sponge) only if the impedance is found not to be optimal, to improve current flow. In this experiment, only 1 stimulating electrode and 1 reference electrode will be used. The investigators will target the dorsal anterior cingulate cortex by placing the stimulating electrode at FC1 on the

Date most recently revised (m/d/y): 03/03/2015

Protocol Version (if applicable): 5.0

10-20 EEG system (see Figure 2). The reference electrode will be placed on the contralateral supra-auricular point, at  $T_3$  (see Figure 3). Point  $T_3$  will be located immediately above the superior tip of the participant's pinna. Point  $FC_1$  will be located via scalp measurements: 50% of the way from the participant's nasion to inion will be used as reference point  $C_z$  (see Figure 2), 33% from the nasion to inion will be used as point  $F_z$ , and 50% of the way from  $T_3$  to  $C_z$  will be used as  $C_3$ .  $FC_1$  will be 50% of the way from  $C_3$  to  $F_z$ . Active tDCS, i.e. anodal or cathodal, will be applied during the session. The device will deliver a maximum of 2 mA (2.55 mA/cm^2) of direct current stimulation for twenty (20) minutes which is controlled by a timer on the device.

[figure not shown]

Figure 2. 10-20 EEG System

[figure not shown]

Figure 3. 10-20 EEG System

In the sham condition, the current paradigm will consist of 40 seconds of stimulation at 1mA and then 19 minutes and 20 seconds of stimulation averaging no more than 0.002mA. This procedure allows for participants to detect the associated tingling sensation at the beginning of the session, making participants more likely to believe that they are receiving active stimulation and the short duration is not expected to have any effect on brain function.

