## **C. Experimental Method**

### **C1. Brief Description of Subjects**

Participants will be aged over 18 years old with a diagnosis of chronic low back pain based on the inclusion criteria (see below) by a referring physician. Participants will be of any racial or ethnic group and of either sex. A questionnaire will be administered to screen for possible contraindications for tDCS (see exclusion criteria). We will consent up to thirty (30) volunteers with a goal of enrolling twenty (20) participants, ten (10) in the treatment group and ten (10) in the control group.

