#### **Inclusion Criteria:**

1. At least eighteen (18) years old;
2. Chronic Low Back Pain - must be present for  $\geq 6$  months duration in the lumbar region, present more than half the days of the month, and on average be at a moderate level of severity in the last month ( $\geq 4$  on the DVPRS scale of pain intensity from 0 (no pain) to 10 (worst pain imaginable).
3. At least one trial of physician recommended medication (i.e. acetaminophen, NSAIDS, skeletal muscle relaxants)
4. Pre-existing opioid and non-opioid pain medication must be non-existent or stable (medications have not changed for one month)
5. Be able to understand, read and write English.
6. If female and of childbearing age, agree to use acceptable birth control during the study

Date most recently revised (m/d/y): 03/03/2015

Protocol Version (if applicable): 5.0

treatment period (oral contraceptives, history of tubal ligation, history of a hysterectomy, or a reliable barrier method) during the study treatment period.

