**Exclusion Criteria:**

1. Lifetime DSM-IV diagnosis of bipolar disorder, schizophrenia, or other chronic psychotic condition;
2. Current DSM-IV diagnosis of substance dependence for alcohol, sedative/ hypnotic drugs, stimulants, or cocaine;
3. Current cancer, infection, or inflammatory arthritis
4. Broken skin or other lesions in the area of the electrodes
5. Uncontrolled medical problems, such as diabetes mellitus, hypertension, pulmonary or airway disease, heart failure, coronary artery disease, or any other condition that poses a risk for the subject during participation.
6. Presence of metal in the cranial cavity
7. Holes in the skull made by trauma or surgery
8. Pacemakers, medication pumps, and other implanted electronic hardware;
9. Pregnancy

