**Risks due to tDCS:** There is some inherent risk with tDCS. Mainly there is a risk of skin irritation where the electrodes are attached to the scalp, which in the literature has been mostly limited to transitory redness. No toxic effects have been found, and the procedure carries few risks (Brunoni, et al., 2012). At the levels we are proposing, only a few publications report minor injuries, and the stimulation is widely considered to be “safe” (Bikson, et al., 2009). In rare cases, when skin around stimulation sites was non-intact, or when the stimulation was delivered for a long time without proper conductive solutions being applied to the electrodes, a few minor burns and skin lesions have been observed (Frank, et al., 2010). If electrodes/sponges are placed over preexisting skin lesions, such as vascular moles and angiomas there may be a greater conductance than the surrounding skin, increasing the risk of irritation or possible burns. Care is thus taken to exclude potential participants who exhibit broken or marked skin near the sites of the electrodes and to avoid abrading the skin prior to placing the electrodes (Loo et al. 2011). The electrodes in this study are soaked in normal saline. A study using the same amperage proposed in this protocol found no mood or cognitive changes due to tDCS (Iyer, et al., 2005). Transient, very rare post-tDCS effects have been found to include mild headaches, nausea, and insomnia (Poreisz, et al., 2007). In a prior study conducted by Drs. [name] and [name], eight of 40 participants reported sensations of itching, tingling, or burning under the tDCS electrodes; one participant reported mild dizziness. These sensations were consistent with those commonly reported for tDCS (Brunoni, et al., 2012). Less well-studied is the possibility of negative effects of tDCS on cognition and mood. A study using the same current amplitude as proposed in this protocol found no mood or cognitive changes due to tDCS, but this was with a single stimulation session (Iyer, et al., 2005). Several studies have used multiple sessions of tDCS of different brain regions successfully to reduce pain intensity from acute pain, neuropathic pain, and chronic pain from fibromyalgia (Antal, et al., 2008; Lefaucher, et al., 2008; Fregni et al. 2006) without significant adverse effects. Another potential concern is the risk of an undesired synergistic effect between a participant’s existing medication and tDCS. There are some reports in the literature of isolated instances of hypomanic or manic symptoms, typically noted with a longer treatment course than proposed in the current study or in patients with pre-existing bipolar diagnoses (Brunoni, et al., 2013; Galvez, et al., 2011) diagnosed bipolar disorder is an exclusion criterion for the present study. Nonetheless, comprehensive clinical studies quantifying the risk more precisely are clearly lacking. For the present study, participants will be closely monitored throughout the study to assess for any such effects. Participants will also be specifically instructed to tell the research staff if they notice an unwanted change in mood.

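### Previous tDCS exposure is neither excluded nor recorded, although the sham relies on brief initial tingling being taken for treatment: a possible threat to the blind, of unknown and probably small size

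*Combined protocol and SAP*

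**What the plan says.** **The two conditions.** Under tDCS Details in C3, the active condition is described thus: "The device will deliver a maximum of 2 mA", applied for twenty minutes. The sham is "40 seconds of stimulation at 1mA and then 19 minutes and 20 seconds of stimulation averaging no more than 0.002mA". Its stated purpose is to make participants more likely to think they are on active treatment: "This procedure allows for participants to detect the associated tingling sensation at the beginning of the session".

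**Who is admitted.** Section 3.A lists six inclusion and nine exclusion criteria. The only inclusion criterion on past treatment concerns drugs: "At least one trial of physician recommended medication". The exclusion criterion closest to devices is "Pacemakers, medication pumps, and other implanted electronic hardware". Neither list mentions earlier tDCS or any other brain stimulation. C1 describes a screening questionnaire for tDCS contraindications and refers to the exclusion list for its content. The eligibility list in the advertisement (section 8) is also silent.

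**Design and blinding.** C2 assigns each participant to one condition for all ten sessions, with participants and outcome raters blinded. C3 has participants guess their treatment, as a check on the blind, after the first session. The guess is not repeated in the text on later sessions, does not appear in Table 1, and has no analysis in C4. The Credibility Expectancy Questionnaire (CEQ) is given at sessions 1 and 10.

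**The concern.** The sham is meant to persuade through a short sensation at the start. A participant with no earlier session has nothing to judge it by. Someone who has had a full active session elsewhere may have a reference for its strength and duration, and ten sessions give ten chances to compare.

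The distress, avoidance and disability outcomes are all questionnaires, and hypotheses 1.1 and 1.2 predict improvement with active but not with sham. If a participant recognises the arm and expectation acts in the usual direction, active reports improve and sham reports worsen. Randomisation tends to balance experienced people between arms, but it does not cancel an effect that has opposite signs in the two arms.

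With 10 per arm, one participant is 10% of an arm. Because prior exposure is not recorded, the analysis could not trace a failed blind to this cause.

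**Working it through.** The protocol has no power analysis (C4), so there is no planned figure to reproduce. The checks below use the stimulation settings in tDCS Details, the sample size in C1 and the prior-study count in 3.C. All other inputs are marked as assumptions.

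**1. How the conditions differ**
- Session length: 40 s + (19 × 60 + 20) s = 40 + 1,160 = 1,200 s = 20 min. Both arms last equally long, so session length does not reveal the arm.
- Peak current: 1 mA / 2 mA = 50% of the active maximum.
- Time at that current: 40 / 1,200 = 3.3% of the session.
- Charge: active 2 × 1,200 = 2,400 mC at most; sham 1 × 40 + 0.002 × 1,160 = 42.3 mC at most, or 1.8% of the active maximum.

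The sham is therefore weaker, and the phase that participants are meant to feel is much briefer.

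**2. What is known about sensation**

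Section 3.C reports, from a prior study, that "eight of 40 participants reported sensations of itching, tingling, or burning under the tDCS electrodes". That is 8/40 = 20% (exact 95% interval 9.1% to 35.6%). It does not say how many of the 40 received active current, at what intensity, or in what population.

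**3. Possible bias**

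Let *k* of the 20 participants be experienced and recognise their arm. Let *b* be the shift in the active-minus-sham contrast that recognition produces, half of it in each direction. One such person moves the mean of his or her arm by (1/10) × (b/2) = b/20, so the bias is k × b/20. The values of *k* and *b* are assumptions.

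The standard error of a difference in means at 10 per arm is √(2/10) = 0.447 SD. A normal approximation then gives the type I error of a nominal two-sided 5% test. (The protocol states no significance level; 5% is assumed.)

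| k of 20 | Bias, b = 0.5 SD | Bias, b = 1.0 SD | Type I error |
|---|---|---|---|
| 0 | 0 | 0 | 5.0% |
| 1 | 0.025 SD | 0.05 SD | 5.0% to 5.1% |
| 2 | 0.05 SD | 0.10 SD | 5.1% to 5.6% |
| 4 | 0.10 SD | 0.20 SD | 5.6% to 7.3% |

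**4. Would the treatment guess reveal it?**

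Assume that experienced participants always guess correctly and the others are right half the time. Under pure chance, 15 or more correct of 20 has probability 2.1%.

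| k of 20 | Expected correct | P(15 or more correct) |
|---|---|---|
| 1 | 52.5% | 3.2% |
| 2 | 55% | 4.8% |
| 4 | 60% | 10.5% |

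A pooled guess would seldom expose a problem of this kind at this sample size.

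**The case against.** **The prior study proves little.** A reader might infer from 3.C that the investigators have already stimulated 40 people who could now enter this trial. The documents do not say so. They do not give the number who had active current, do not say that any had back pain, and do not place them in this recruitment pool. That the study is the group's own is clear only from context. This objection stands, and the point does not depend on that study.

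**Previous exposure does not make someone eligible.** It merely fails to disqualify. A candidate must still meet the criteria on duration, frequency and severity of pain, the past medication trial and stable medication. This stands.

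**Recognition is not shown.** A reader might conclude that experienced participants can tell their arm. The documents hold no data on this, and 32 of the 40 in the cited study were not among those reporting itching, tingling or burning. Session length gives nothing away. Recognition is plausible and no more.

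**Few experienced people may come forward.** Recruitment is by referral and advertisement, and the advertisement calls the device new. Nothing suggests that a sizeable share would have had tDCS. This stands.

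**Direction is assumed.** Someone whose earlier course did not help might expect less from active treatment. For hypotheses 1.3 and 2.3, which predict no change in pain intensity, bias toward improvement would work against the hypothesis.

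**Safeguards exist.** The treatment guess and the CEQ bear directly on this mechanism, and the investigators judge whether each volunteer is appropriate. But the guess and the CEQ can detect a weak blind and cannot prevent one, and neither can be related to prior exposure if it is not recorded.

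**The remedy is partial.** Participants new to tDCS could also notice the sensation ending early. An eligibility rule does not address that. It closes one route only.

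**Conclusion.** The gap is real: previous tDCS is neither a bar to entry nor a recorded item, while the blind relies on a short, weaker sensation being taken for treatment. What follows is a possible bias in the self-reported contrasts, of unknown and probably small size.

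For one or two experienced participants of 20 it is about 0.025 to 0.10 SD, which leaves a nominal 5% test at about 5.0% to 5.6% and is small beside a standard error of 0.447 SD. This rests on three assumptions: the number of experienced participants, that they recognise their arm, and a shift of 0.5 to 1.0 SD in the expected direction. If none enrol, the bias is zero.

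A reader might be drawn to a larger figure, such as 0.1 to 0.3 SD. At a 1.0 SD shift that needs 2 to 6 of the 20 to be experienced and to recognise their arm (2/20 × 1.0 = 0.1; 6/20 × 1.0 = 0.3). Nothing in the documents suggests the upper part of that range.

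This is a minor point in a trial declared exploratory. It is worth acting on because it costs little and cannot be repaired after enrolment.

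**What to change.** Add one exclusion criterion to 3.A, for example: previous tDCS in which active stimulation was given or the assigned arm is unknown. People known to have had only sham lack the active reference sensation and need not be excluded. Ask the question in the contraindication questionnaire described in C1.

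If the sponsor prefers not to exclude, the minimum is to record prior tDCS exposure at screening (none, active, sham, unknown), and to state in C4 that the treatment guess will be reported by arm and by prior exposure.

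The cost is one criterion and one screening question, with a small loss of otherwise eligible volunteers from the 30 who may be consented to reach 20. Recording alone loses none. Neither option changes the stimulation or the visit schedule.
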